## 8.3 Adjuvant Dose Modifications Based on Adverse Events (All Arms)

## General guidance:

- a Atezolizumab may be withheld for a longer period of time (i.e., > 12 weeks after event onset) to allow for corticosteroids (if initiated) to be reduced to the equivalent of  $\leq 10$  mg/day oral prednisone. The acceptable length of the extended period of time must be based on the investigator's benefit-risk assessment and in alignment with the protocol requirements for the duration of treatment and documented by the investigator
- b If corticosteroids have been initiated, they must be tapered over  $\geq 1$  month to the equivalent of  $\leq 10$  mg/day oral prednisone before atezolizumab can be resumed
- c Resumption of atezolizumab may be considered in patients who are deriving benefit and have fully recovered from the immune-mediated event. The decision to re-challenge patients with atezolizumab should be based on the investigator's benefit-risk assessment and documented by the investigator

CTCAE System/Organ/Class (SOC)	ADVERSE EVENTS/SYMPTOMS	Atezolizumab
Cardiac disorders	Immune-mediated myocarditis OR Immune-mediated pericardial disorders Grades 2-4	Permanently discontinue atezolizumab
Endocrine disorders	Adrenal insufficiency	See Table 8.31 for management of atezolizumab See Section 9.0 for suggested supportive care
Endocrine disorders	Hyperglycemia	See Table 8.31 for management of atezolizumab See Section 9.0 for suggested supportive care
Endocrine disorder	Hyperthyroidism	See Table 8.31 for management of atezolizumab See Section 9.0 for suggested supportive care
Endocrine disorders	Hypophysitis	See Table 8.31 for management of atezolizumab See Section 9.0 for suggested supportive care
Eye disorders	Eye disorders, other specify: Ocular event, Grade 1	Continue atezolizumab See Section 9.6 for suggested supportive care If symptoms persist, treat as a Grade 2 event
	Eye disorders, other specify: Ocular event Grade 2	Withhold atezolizumab for up to 12 weeks after event onset (a) See Section 9.6 for suggested supportive care If event resolves to Grade 1 or better, resume atezolizumab(b) If event does not resolve to Grade 1 or better while withholding atezolizumab, permanently discontinue atezolizumab (c)
	Eye disorders, other specify: Ocular event Grade 3-4	Permanently discontinue atezolizumab (c) See Section 9.6 for suggested supportive care

CTCAE System/Organ/Class (SOC)	ADVERSE EVENTS/SYMPTOMS	Atezolizumab
Gastrointestinal Disorders	Diarrhea/Colitis Grade 2	Withhold atezolizumab for up to 12 weeks after event onset (a) See Section 9.0 for suggested supportive care If event resolves to Grade 1 or better, resume atezolizumab (b) If event does not resolve to Grade 1 or better while withholding atezolizumab, permanently discontinue atezolizumab (c)
	Grade 3	Withhold atezolizumab for up to 12 weeks after event onset (a) If event resolves to Grade 1 or better, resume atezolizumab (b) If event does not resolve to Grade 1 or better while withholding atezolizumab, permanently discontinue atezolizumab (c)
	Grade 4	Permanently discontinue atezolizumab
Gastrointestinal disorders	Pancreatitis (immune-mediated) Grade 2 or 3	Withhold atezolizumab for up to 12 weeks after event onset (a) If event resolves to Grade 1 or better, resume atezolizumab (b) If event does not resolve to Grade 1 or better while withholding atezolizumab, permanently discontinue atezolizumab (c) For recurrent events, permanently discontinue atezolizumab (See Investigations/Lipase increased or serum amylase increased below)
	Grade 4	Permanently discontinue atezolizumab
General disorders and administration site conditions	Infusion-related reaction Grade 3-4	Discontinue
Infections and infestations	Myelitis, immune-mediated Grade 2-4	Permanently discontinue atezolizumab See Section 9.0 for suggested supportive care
Immune system disorders	Allergic reaction or Anaphylaxis Grade 2	Hold and resume when symptoms resolve to ≤Grade 1 Pre-treatment required prior to subsequent doses (Section 9.0)
	Grade 3-4	Discontinue
Immune system disorders	Immune system disorders, other (specify): Immune-related myasthenic syndrome/myasthenia gravis, Guillain-Barré, or meningoencephalitis	Permanently discontinue atezolizumab

CTCAE System/Organ/Class (SOC)	ADVERSE EVENTS/SYMPTOMS	Atezolizumab
Investigations For patients without hepatocellular carcinoma (HCC)	Aspartate aminotransferase increased or Alanine aminotransferase increased or Blood bilirubin increased Grade 1	Continue, and monitor LFTs more frequently until return to baseline values
	Grade 2	Monitor LFTs more frequently until return to baseline values For events lasting >5 days Withhold atezolizumab for up to 12 weeks after event onset (a) See Section 9.0 for suggested supportive care Resume if event resolves to ≤Grade 1 (b) If event does not resolve to Grade 1 or better while withholding atezolizumab, permanently discontinue atezolizumab (c)
	Grade 3-4	Permanently discontinue atezolizumab See Section 9.0 for suggested supportive care
	Aspartate aminotransferase increased or Alanine aminotransferase increased If within normal limits at baseline and increases to ≥Grade 1	Withhold atezolizumab for up to 12 weeks after event onset (a) Monitor LFTs more frequently until return to baseline values If event resolves to baseline or to Grade 1 or better, resume atezolizumab (b) If event does not resolve to baseline or to Grade 1 or better while withholding atezolizumab, permanently discontinue atezolizumab (c)
Investigations For patients with hepatocellular carcinoma (HCC)	Aspartate aminotransferase increased or Alanine aminotransferase increased >10 x ULN or Blood bilirubin increased Total bilirubin >3 x ULN	Permanently discontinue atezolizumab See Section 9.6 for suggested supportive care
	Lipase increased or Serum amylase increased Grade 2 (>1.5-2.0 x ULN)	Continue atezolizumab
	Grade 3 (>2.0- 5.0 x ULN)	Withhold atezolizumab for up to 12 weeks after event onset (a) If event resolves to Grade 1 or better, resume atezolizumab If event does not resolve to Grade 1 or better while withholding atezolizumab, permanently discontinue atezolizumab For recurrent events, permanently discontinue atezolizumab (c)
Renal and urinary disorders	Acute kidney injury Grade 2	Withhold atezolizumab for up to 12 weeks after event onset If event resolves to Grade 1 or better, resume atezolizumab (b) If event does not resolve to Grade 1 or better while withholding atezolizumab, permanently discontinue atezolizumab (c)
	Grade 3-4	Permanently discontinue atezolizumab

CTCAE System/Organ/Class (SOC)	ADVERSE EVENTS/SYMPTOMS	Atezolizumab
Respiratory, thoracic and mediastinal disorders	Pneumonitis Grade 1	Continue atezolizumab and monitor closely For Grade 1 pneumonitis, consider withholding atezolizumab
	Grade 2	Withhold atezolizumab for up to 12 weeks after event onset (a) See Section 9.6 for suggested supportive care If event resolves to Grade 1 or better, resume atezolizumab (b) If event does not resolve to Grade 1 or better while withholding atezolizumab, permanently discontinue atezolizumab (c, d) For recurrent events, or events with no improvement after 48–72 hours of corticosteroids, treat as a Grade 3 or 4 event
	Grade 3-4	Permanently discontinue atezolizumab (c) See Section 9.6 for suggested supportive care In case of pneumonitis, atezolizumab should not be resumed after permanent discontinuation
Skin and subcutaneous tissue disorders	Rash acneiform Grade 3	Hold and initiate supportive care (per Section 9.0) Resume when symptoms resolve to ≤Grade 1
	Grade 4	Hold until ≤Grade 1 Resume at same dose once ≤Grade 1
Skin and subcutaneous tissue disorders	Rash maculo-papular Grade 2	Continue and initiate supportive care per Section 9.0
	Grade 3	Withhold atezolizumab for up to 12 weeks after event onset See Section 9.0 for suggested supportive care If event resolves to Grade 1 or better, resume atezolizumab If event does not resolve to Grade 1 or better while withholding atezolizumab, permanently discontinue atezolizumab For recurrent events, permanently discontinue atezolizumab (c)
	Grade 4	Permanently discontinue atezolizumab (c)
Skin and subcutaneous tissue disorders	Stevens-Johnson syndrome (SJS) or Toxic epidermal necrolysis (TEN)	Withhold atezolizumab for suspected Stevens-Johnson syndrome or toxic epidermal necrolysis If Stevens-Johnson syndrome or toxic epidermal necrolysis is confirmed, permanently discontinue atezolizumab See Section 9.0 for suggested supportive care
Other Adverse Events	Grade 3	Withhold atezolizumab for up to 12 weeks after event onset See Section 9.0 for suggested supportive care If event resolves to Grade 1 or better, resume atezolizumab If event does not resolve to Grade 1 or better while withholding atezolizumab, permanently discontinue atezolizumab For recurrent events, permanently discontinue atezolizumab (c)
	Grade 4	Permanently discontinue atezolizumab (c)

## 8.31 Actions for CTCAE SOC Endocrine Disorders

## General guidance:

- a Atezolizumab may be withheld for a longer period of time (i.e., > 12 weeks after event onset) to allow for corticosteroids (if initiated) to be reduced to the equivalent of  $\leq 10$  mg/day oral prednisone. The acceptable length of the extended period of time must be based on the investigator's benefit-risk assessment and in alignment with the protocol requirements for the duration of treatment and documented by the investigator
- b If corticosteroids have been initiated, they must be tapered over  $\geq 1$  month to the equivalent of  $\leq 10$  mg/day oral prednisone before atezolizumab can be resumed
- c Resumption of atezolizumab may be considered in patients who are deriving benefit and have fully recovered from the immune-mediated event. The decision to re-challenge patients with atezolizumab should be based on the investigator's benefit-risk assessment and documented by the investigator

Endocrine Disorders Event	Action
Adrenal insufficiency symptomatic Grades 2-4	
 
Withhold atezolizumab for up to 12 weeks after event onset (a)
 
See Section 9.6 for suggested supportive care
 
If event resolves to Grade 1 or better and patient is stable on replacement therapy, resume atezolizumab (b)
 
If event does not resolve to Grade 1 or better or patient is not stable on replacement therapy while withholding atezolizumab, permanently discontinue atezolizumab (c)
 

Hypothyroidism Grade 1	
 
Continue atezolizumab
 
Monitor TSH closely
 
See Section 9.6 for suggested supportive care
 

Grade 2	
 
Consider withholding atezolizumab
 
See Section 9.6 for suggested supportive care
 
Monitor TSH closely
 
Resume atezolizumab when symptoms are controlled, and thyroid function is improving
 

Grade 3 and 4	
 
Withhold atezolizumab
 
See Section 9.6 for suggested supportive care
 
Monitor TSH closely
 
Resume atezolizumab when symptoms are controlled, and thyroid function is improving
 
Permanently discontinue atezolizumab (c)
 

Endocrine Disorders Event	Action
Hyperthyroidism Grade 1	TSH <math>\geq</math>01 mU/L and <math><</math>05 mU/L: 
 
Continue atezolizumab
 
See Section 9.6 for suggested supportive care
 
Consider patient referral to endocrinologist
 
 TSH <math><</math>01 mU/L: 
 
Follow guidelines for symptomatic hyperthyroidism
 
See Section 9.6 for suggested supportive care
 

Grade 2	
 
Consider withholding atezolizumab
 
See Section 9.6 for suggested supportive care
 
Resume atezolizumab when symptoms are controlled, and thyroid function is improving
 

Grade 3 and 4	
 
Withhold atezolizumab
 
See Section 9.6 for suggested supportive care
 
Resume atezolizumab when symptoms are controlled, and thyroid function is improving
 
Permanently discontinue atezolizumab c
 

Hyperglycemia Grade 1 or 2	
 
Continue atezolizumab
 
Investigate for diabetes: 
 
If patient has Type 1 diabetes, treat as a Grade 3 event
 
If patient does not have Type 1 diabetes, treat per institutional guidelines
 
 
 

Grade 3 or 4	
 
Withhold atezolizumab
 
Resume atezolizumab when symptoms resolve, and glucose levels are stable
 

Hypophysitis (pan-hypopituitarism) Grade 2 or 3	
 
Withhold atezolizumab for up to 12 weeks after event onset (a)
 
See Section 9.6 for suggested supportive care
 
If event resolves to Grade 1 or better, resume atezolizumab (b)
 
If event does not resolve to Grade 1 or better while withholding atezolizumab, permanently discontinue atezolizumab (c)
 
For recurrent hypophysitis, treat as a Grade 4 event
 

Grade 4	
 
Permanently discontinue atezolizumab (c)
 
See Section 9.6 for suggested supportive care
 

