### 8.1 Dose Levels (Based on Adverse Events in Tables 8.2 and 8.3)

Please note there are no dose reductions for atezolizumab or tiragolumab

\*Dose level 0 refers to the starting dose.

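### Section 8.31: the adjuvant Grade 3–4 hypothyroidism and hyperthyroidism cells say both to resume and to permanently stop atezolizumab, with no trigger for the stop

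*Combined protocol and SAP*

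**What the plan says.** Section 8.31 governs atezolizumab for endocrine events in the adjuvant phase, in all arms. Its Grade 3 and 4 cell for hypothyroidism and its Grade 3 and 4 cell for hyperthyroidism share the same core. Each begins with an instruction to withhold. Each then gives a resume bullet, "Resume atezolizumab when symptoms are controlled, and thyroid function is improving". Each ends with a stop bullet, which in the hyperthyroidism cell reads "Permanently discontinue atezolizumab c"; the hypothyroidism cell has the same words with the footnote letter in parentheses.

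Footnote (c), in the general guidance above the table, says: "Resumption of atezolizumab may be considered in patients who are deriving benefit and have fully recovered from the immune-mediated event". It leaves the decision to a documented benefit-risk assessment by the investigator.

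Two other cells in the table also list both actions, but state when each applies. For adrenal insufficiency, the stop applies if the event does not resolve to Grade 1 or better "or patient is not stable on replacement therapy while withholding atezolizumab, permanently discontinue atezolizumab". For hypophysitis Grade 2 or 3: "If event does not resolve to Grade 1 or better while withholding atezolizumab, permanently discontinue atezolizumab (c").

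Two general provisions bear on this. Section 8.0 says the adjuvant modifications are guidelines. Section 8.13 says atezolizumab should be discontinued if withheld for more than 105 days, with exceptions for steroid taper and for investigator-judged benefit.

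**The concern.** The cell gives two incompatible end actions. The resume bullet has a condition; the stop bullet has none, so read literally it applies to every Grade 3 or 4 event and cancels the bullet above it. The two bullets also imply different bars for giving the drug again. Improving thyroid function is enough under the resume bullet. Footnote (c), which belongs to the stop bullet, requires full recovery plus evidence of benefit.

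What is at stake is patient safety and consistent dosing after a severe or life-threatening thyroid event. Two sites with the same patient could make opposite decisions, each citing a bullet in the same cell.

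**Working it through.** The plan states no figure on this point, so the check is a comparison of text. The inputs are the cells of Section 8.31, its footnotes, and Sections 8.0, 8.13 and 8.3.

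**Step 1. Cells in 8.31 that list both actions, with two reference cells.**

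| Cell | Limit on hold | Resume when | Stop permanently when |
|---|---|---|---|
| Adrenal insufficiency, Grades 2–4 | 12 weeks (a) | Grade 1 or better and stable on replacement | Either condition not met (c) |
| Hypophysitis, Grade 2 or 3 | 12 weeks (a) | Grade 1 or better | Not resolved to Grade 1 (c) |
| Hypothyroidism, Grade 3 and 4 | None in cell | Symptoms controlled, function improving | No trigger (c) |
| Hyperthyroidism, Grade 3 and 4 | None in cell | Symptoms controlled, function improving | No trigger (c) |
| *Reference:* hyperglycemia, Grade 3 or 4 | None in cell | Symptoms resolved, glucose stable | No permanent stop |
| *Reference:* hypophysitis, Grade 4 | Not applicable | Only under (c) | Always (c) |

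Four cells list both actions and two of the four lack a trigger for the stop. The two reference cells show that the table can also express one action alone. The thyroid cells fit none of these patterns.

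**Step 2. What each available reading does.** Take a patient whose symptoms are controlled and whose thyroid function is improving but not yet normal.

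| Reading of the cell | Grade 3 event | Grade 4 event |
|---|---|---|
| Stop only if the event is not controlled (adrenal pattern) | Re-dose | Re-dose |
| Resume after Grade 3, stop at Grade 4 | Re-dose | Stop |
| Stop at both grades, re-challenge only under (c) | Stop until fully recovered | Stop until fully recovered |

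The rest of the plan does not choose. A Grade 4 permanent stop is the rule for hypophysitis in 8.31, and for diarrhea/colitis, pancreatitis, maculo-papular rash and other adverse events in 8.3. Against that, the adrenal and hyperglycemia cells of 8.31 let a Grade 4 event resume.

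**Step 3. Does Section 8.13 settle it?** That section sits under the heading "Dose Levels (Based on Adverse Events in Tables 8.2 and 8.3"), so it reaches the adjuvant phase. Its limit is 105 / 21 = 5 cycles. The adjuvant course is at most 8 × 21 = 168 days, so the limit is 105 / 168 = 62.5% of the course (±3-day windows ignored). It says nothing about which bullet governs before day 105, and after that it still allows resumption if the investigator expects benefit. It is a backstop and supplies no trigger.

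**Step 4. Is it a layout accident?** The same resume-then-stop pair appears in two separate cells, which makes a lost condition from table layout unlikely.

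**The case against.** The strongest reply is that these are guidelines under Section 8.0, that footnote (c) already lets an investigator re-challenge, and that a competent endocrinologist would read the stop bullet as applying to events that do not come under control. That limits the consequence, and it stands as far as severity goes. It does not remove the contradiction: guidance still needs one default, and the grade-based reading is equally available.

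Several stronger conclusions are tempting, and the documents do not support them.

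- *A reader might infer that the cells have no condition or time limit at all.* The resume bullet has a condition, and Section 8.13 sets an outside limit.
- *A reader might treat the missing 12-week cap as an error.* The adrenal and hypophysitis Grade 2–3 cells do say "Withhold atezolizumab for up to 12 weeks after event onset (a"), but hyperglycemia Grade 3–4 and both Grade 2 thyroid cells have no cap either. Uncapped holds are an accepted pattern in this table.
- *A reader might count every remaining dose as lost under the stop reading.* Footnote (c) permits re-challenge, so the readings differ in the threshold for re-dosing; the stop need not be irrevocable.
- *A reader might see a further conflict with Section 9.642*, which allows isolated hypothyroidism to be managed without interrupting treatment. Section 9.51 sends interruption decisions to Sections 8.2–8.3, which settles it.
- *A reader might contrast the simpler neoadjuvant thyroid rule.* Section 8.0 gives the two phases different status, so a different rule is not a contradiction.
- *A reader might extend the point to the AST/ALT row for normal baseline values in 8.3.* Its place between the blocks with and without hepatocellular carcinoma cannot be relied on from the table as read.

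**Conclusion.** The point holds in a narrow form. Both adjuvant Grade 3–4 thyroid cells are wrong as written: they pair a conditional resume with an unconditional permanent stop, and the two carry different bars for re-dosing. Severity is minor.

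The number of patients cannot be computed. Section 15.17 lists hypothyroidism and hyperthyroidism among events seen in 1–10% of patients and does not split them by grade, so no Grade 3–4 rate follows. That few patients are affected is a judgement from those all-grade figures and the small arms.

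A reader might infer damage to the efficacy endpoints. None is claimed. pCR is read at surgery, before adjuvant treatment begins, and Section 16.12 includes in the RFS analysis everyone who began adjuvant treatment. The conclusion assumes that the bullets in the two cells are complete as they stand.

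**What to change.** In both Grade 3 and 4 thyroid cells, keep the withhold and resume bullets and make the last bullet conditional. For example: *stop atezolizumab permanently, subject to footnote (c), if symptoms remain uncontrolled or thyroid function fails to improve during the hold.*

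Before issuing it, the clinical leads and drug supplier should confirm whether Grade 4 should instead be a permanent stop with re-challenge only under (c). If so, split the cell into a Grade 3 row with the conditional wording and a Grade 4 row with the stop alone. No 12-week cap is needed, and Sections 8.13 and 9.642 can stay as they are.

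The cost is one edited bullet in each of two cells, sent to sites as a memo now and carried into the next amendment. There is no change to data collection, sample size or analysis.

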## **9.0 Ancillary Treatment/Supportive Care**

### **9.1 Full supportive care**

Patients should receive full supportive care while on this study. This care includes blood product support, antibiotic treatment, and treatment of other newly diagnosed or concurrent medical conditions. All blood products and concomitant medications such as antidiarrheals, analgesics, and/or antiemetics received from the first day of study treatment administration until 28 days after the final dose will be recorded in the medical records.

### **9.2 Hypersensitivity reaction**

Patients do not require premedication prior to study treatment, as hypersensitivity reaction is not expected. In the unlikely event of a hypersensitivity reaction, treatment with antihistamines, H2 blockers, and corticosteroids is recommended. Patients should be pre-medicated with the typical regimen for subsequent cycles.

If anaphylaxis is suspected, follow institutional guidelines, including discontinuing treatment infusion and instituting appropriate supportive measures.

### **9.3 Concurrent enrollment in other studies**

Patients may not enroll in a different clinical study, including Cancer Control studies, in which investigational procedures or agents are being used, while participating in this study.

### **9.4 Concurrent radiation therapy**

Patients must terminate study treatment if they are to receive radiation therapy for palliative reasons as it impacts evaluation of study endpoints.

### **9.5 General patient monitoring and supportive care guidelines**

9.51 Patients should be carefully monitored during the treatment phase and then followed appropriately. Decisions for retreatment or dose modifications/interruption should follow the guidelines in Sections 8.2-8.3.

9.52 Patients who have an ongoing study agent-related serious adverse event upon study completion or at discontinuation from the study will be contacted by the treating physician or his/her designee at least every 2 weeks until the event is resolved or determined to be irreversible.

### **9.6 Side effect management for atezolizumab adverse events**

These instructions are to be regarded as guidelines for managing toxicity that occurs with atezolizumab therapy and should not replace clinical judgement (e.g., patients with Grade 1 rash may require systemic steroids).

#### **9.61 Diarrhea/Colitis**

All events of diarrhea or colitis should be thoroughly evaluated for more common etiologies other than drug-induced effects.

For events of significant duration or magnitude or associated with signs of systemic inflammation or acute-phase reactants, (e.g., increased C-reactive protein, platelet count, or bandemia): Perform sigmoidoscopy (or colonoscopy, if appropriate) with colonic biopsy, with three to five specimens for standard paraffin block to check for inflammation and lymphocytic infiltrates to confirm colitis diagnosis..

- 9.611 Grade 1  
Patients may be managed symptomatically. Instruct patients to report any increase in stools.  
Endoscopy is recommended if symptoms persist >7 days.  
Monitor closely.
- 9.612 Grade 2  
Initiate symptomatic treatment.  
If strong clinical suspicion for immune-mediated colitis, start empiric IV steroids while waiting for definitive diagnosis  
Patient referral to GI specialist is recommended  
For recurrent events or events that persist >5 days, initiate treatment with corticosteroids equivalent to 1–2 mg/kg/day oral prednisone. If the event does not improve within 48 hours after initiating corticosteroids, consider adding an immunosuppressive agent.
- 9.613 Grade 3  
Refer patient to GI specialist for evaluation and confirmatory biopsy  
Initiate treatment with corticosteroids equivalent to 1-2 mg/kg/day IV methylprednisolone and convert to 1-2 mg/kg/day oral prednisone or equivalent upon improvement.  
If the event does not improve within 48 hours after initiating corticosteroids, consider adding an immunosuppressive agent.
- 9.614 Grade 4  
Refer patient to GI specialist for evaluation and confirmatory biopsy.  
Initiate treatment with corticosteroids equivalent to 1–2 mg/kg/day IV methylprednisolone and convert to 1–2 mg/kg/day oral prednisone or equivalent upon improvement.  
If event does not improve within 48 hours after initiating corticosteroids, consider adding an immunosuppressive agent.

**Do NOT administer loperamide in patients with  $\geq$ Grade 2 diarrhea as this may cause toxic megacolon and/or perforation.**

**If at any time patients experience diarrhea with the following symptoms: fever or abdominal pain patients should have a CT scan of the abdomen to rule out perforation. Emergent surgical evaluation should be performed if perforation is found. If a patient has bloody diarrhea, a Gastroenterology consult should be obtained. A Gastroenterology consult should be obtained if provider is considering infliximab for treatment of colitis.**

For all patients- assess hydration status and monitor electrolytes, including magnesium.

- 9.62 Skin and subcutaneous tissue disorders  
The majority of cases of rash reported with the use of atezolizumab were mild in severity and self-limiting, with or without pruritus. Although uncommon, cases of severe cutaneous adverse reactions such as Stevens-Johnson syndrome and toxic epidermal necrolysis have been reported with atezolizumab. A dermatologist should evaluate persistent and/or severe rash or pruritus. A biopsy should be considered unless contraindicated.

- 9.621 Rash Acneiform  
Consider doxycycline, minocycline, and/or topical steroids (Grade 2), or systemic steroids (Grade 3).
- 9.622 Rash Maculopapular  
Grade 1 or 2- start oral non-sedating daily antihistamine (e.g., cetirizine (Zyrtec®) or loratidine (Claritin®)) and use topical hydrocortisone cream to areas of rash with pruritis. If rash continues to progress, start systemic steroids at 0.5 mg/kg daily.  
Grade 3 or greater. Initiate systemic steroid therapy at 1-2 mg/kg/day of prednisone or equivalent.
- 9.623 Severe Cutaneous Adverse Reactions (SCARs)  
Severe Cutaneous Adverse Reactions (SCARs) are rare but potentially fatal skin toxicities frequently associated with drug use including the immune checkpoint inhibitor class. These include erythema multiforme, acute generalized exanthematous pustulosis, Stevens-Johnson syndrome (SJS), Toxic Epidermal Necrolysis (TEN), and drug rash with eosinophilia and systemic symptoms (DRESS).  
For suspected SCARS, patients should be referred to a specialist (dermatologist, ophthalmologist, or urologist as relevant) for further diagnosis and management.  
Atezolizumab should be withheld for suspected SJS or TEN  
Atezolizumab should be permanently discontinued for any grade of confirmed SJS or TEN  
Exercise caution in patients who have previously experienced a severe or life-threatening skin adverse reaction on prior treatment with other immune-stimulatory anti-cancer agents.
- 9.63 Skin lesion concerning for malignancy  
Refer for biopsy.
- 9.64 Endocrine Events  
Patients with unexplained symptoms such as headache, fatigue, myalgias, impotence, constipation, or mental status changes should be investigated for the presence of thyroid, pituitary, or adrenal endocrinopathies. The patient should be referred to an endocrinologist if an endocrinopathy is suspected. Thyroid-stimulating hormone (TSH) and free triiodothyronine and thyroxine levels should be measured to determine whether thyroid abnormalities are present. Pituitary hormone levels and function tests (e.g., TSH, growth hormone, luteinizing hormone, follicle-stimulating hormone, testosterone, prolactin, adrenocorticotrophic hormone [ACTH] levels, and ACTH stimulation test) and magnetic resonance imaging (MRI) of the brain (with detailed pituitary sections) may help to differentiate primary pituitary insufficiency from primary adrenal insufficiency.
- 9.641 Hyperthyroidism  
Hyperthyroidism is usually self-limiting short-lived, and does not require intervention, unless symptomatic (e.g. tachycardia). If patient experiences tachycardia, treatment with low-dose beta blockade would be indicated.

Monitor TSH every 4 weeks

Consider referring patient to Endocrinology.

For Grade 3-4 Hyperthyroidism:

- Initiate treatment with anti-thyroid drugs such as methimazole or carbimazole as needed.
- Refer to an endocrinologist.

9.642 Hypothyroidism

Isolated hypothyroidism may be managed with replacement therapy without treatment interruption and without corticosteroids.

Monitor TSH closely

Refer patient to Endocrinology if needed.

Admit patient to the hospital for developing myxedema (bradycardia, hypothermia, and altered mental status).

9.643 Immune-Mediated Hypophysitis

Refer patient to Endocrinology for treatment and monitoring.

Perform brain MRI (pituitary protocol) if indicated.

Initiate treatment with corticosteroids equivalent to 1-2 mg/kg/day IV methylprednisolone and convert to 1-2 mg/kg/day oral prednisone or equivalent upon improvement.

Initiate hormone replacement if clinically indicated.

9.644 Immune-Mediated Adrenal Insufficiency

Refer patient to endocrinologist.

Perform appropriate imaging.

Initiate treatment with corticosteroids equivalent to 1–2 mg/kg/day IV methylprednisolone and convert to 1–2 mg/kg/day oral prednisone or equivalent upon improvement.

9.645 Hyperglycemia

Investigate for diabetes. If patient has Type 1 diabetes, treat per institutional guidelines.

Monitor for glucose control.

Grade 3 or 4 Hyperglycemia:

- Initiate treatment with insulin.
- Evaluate for diabetic ketoacidosis and manage per institutional guidelines.

